# 9.4.2.3 Handling of Missing Data

All reasonable efforts will be made to reduce the rate of missing data. Investigators will be trained about the importance of patient retention and full data capture. Also, any reasonable attempts should be made by the Investigators to emphasize continued subject's participation for the full duration of the trial.

## 9.4.2.4 Sensitivity analyses

The following sensitivity analyses are defined to assess the robustness of results on primary endpoints versus adherence to protocol and presence of confouring factors:

Comparison between treatment and control will be performed in the PP population (see section 9.3 for definition) instad of FAS;

Comparison between treatment and control will be performed by means of a Cox regression model, using pre-specified baseline charateristics as covariates (details will be provided in the SAP). The above sensistivity assessemnts will be performed at the time of phase III analysis. Additional sensitivity analyses may be added in the SAP.

## 9.4.2.5 Secondary Efficacy Analyses

Each component of the primary composite endpoints will be evaluated separately, and their 95% C.I. will be reported. In addition to descriptive statistics, all secondary endpoints will be analyzed by appropriate parametric tests depending on the nature of the variable and its distribution. Data transformation might be used in order to satisfy the assumption of normality requested by parametric statistical tests. In case such assumptions are not met, non-parametric counterpart tests will be used. Details will be provided in the SAP.

Change from baseline value (for continuous variables) and shift tables versus baseline (for categorical variables) will also be summarized for all post-baseline visits.

## 9.4.3 Safety Analysis

Treatment-Emergent Adverse Events (TEAEs), Adverse Drug Reactions (ADRs) and Serious Adverse Events (SAEs) will be presented treatment arm (and route of administration if required) in terms of number of AEs and their incidence by System Organ Class (SOC) and Preferred Terms (PT) using MedDRA. Analyses will be provided also by severity and relationship to the treatment. Vital signs and laboratory tests will be presented using descriptive statistics at each available visit. Additionally, the frequency of subjects reporting an abnormal or abnormal clinically significant laboratory value at each available visit will be presented for each laboratory parameter. Shift tables versus baseline will compare abnormal laboratory findings at each post-baseline visit.

# 9.4.4 Analysis of exploratory variables

In addition to descriptive statistics at each available timepoint, explorative variables will be analyzed by means of inferential tests depending on their nature and distribution (all confidence intervals and statistical tests on explorative endpoints are of descriptive nature).

## 9.4.5 Intermediate analyses for DMC

Due to the open-label nature of this trial, an indipendent data monitoring committee is foreseen to provide timely recommendations about the early closures or modifications. This monitoring committee will include 2 to 4 indipendent physicians, supported by a statistician.

Safety and efficacy data will be reviewed on an ongoing basis by a DMC. The DMC will give careful consideration to the appropriateness of trial continuation if there is emerging evidence that Reparixin is harmful. Similarly, DMC may suggest to interrupt one of the routes of administration of Reparixin. In making any recommendations about termination for safety reasons, the totality of data will be considered, including the number of unexpected deaths in the control group, and the available evidence about efficacy and the overall safety profile. Early termination would be considered if the rate of clinically significant post-surgical complications that require reoperation reliably exceeds the rate expected currently in standard practice settings. The DMC will also consider early termination if the quality of conduct of the trial is such that the trial will not be able to provide a timely and reliable answer to the questions it was designed to address.

Primary endpoint data will be evaluated by DMC for identification of early superiority of Reparixin (efficacy) or for an early stop of the trial for futility (nonbinding). During phase II it has been planned to have 1 interim analysis, while 2 interim analyses will be performed during phase III. O'Brien-Fleming spending functions will be used to control the type I and II errors for analyses of primary endpoints. P-values boundaries for efficacy and futility at interim and final analyses for phase 2 and phase 3 are reported in Table 1 and Table 2, respectively. Unplanned DMC interim analyses might be performed. In that case, only safety data will be evaluated.

Analysis	Sample	-	primary endpoint ptide)
Size		Efficacy	Futility
Interim #1	~27	p-value <0.00258	p-value ≥0.23349
Final	48	p-value <0.02400	p-value ≥0.02400

Table 1: O'Brien-Fleming spending functions boundaries for primary analysis in phase II

Table 2: O'Brien-Fleming s	mending functions	boundaries for 1	nrimarv analvsi	s in nhase III
Table 2. O Diren-Freining s	spending functions	boundaries for p	pi mai y anaiysi	s in phase in

Analysis	Sample Size	•	primary endpoint ptide)
	Size	Efficacy	Futility
Interim #1	~60	p-value <0.00296	p-value ≥0.26674
Interim #2	~81	p-value <0.00892	p-value ≥0.09841
Final	111	p-value <0.02151	p-value ≥0.02151

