Death shall always be reported as SAE: anyway, death due to progression of disease would not have a causal relationship to the product, based on Investigator's assessment. The investigator should report the event immediately to the sponsor, but the sponsor will not report the event as expedited to regulatory authority. Cause of death shall always be specified when known.

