3.4 Overview of planned statistical analyses

The study plans for the following statistical analyses:

- Phase 2:
 - Interim analysis for efficacy or futility: this analysis will be conducted by Data Monitoring Committee (DMC) when half of the planned events of primary endpoint of phase 2 has happened;

- Final analysis: this analysis will be conducted when all randomized phase 2 subjects has performed the final visit.
- Phase 3 (in case of success of phase 2):
 - Interim analyses for efficacy or futility: this analysis will be conducted by DMC when approximately 55% and 74% of the planned severe events of primary endpoint of phase 3 has happened;
 - Final analysis: this analysis will be conducted all randomized phase 3 subjects has performed the final visit.
- Analyses for the DMC: these analyses will be produced periodically according to the DMC charter. In addition to the above interim analyses, analyses for safety integrity reviews will be performed according to DMC charter.

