3.5 Efficacy endpoints

3.5.1 Primary endpoints

- Primary Endpoint for phase 2: Composite endpoint of clinical events (the subject requires at least one of the following: supplemental oxygen requirement, invasive mechanical ventilation use, admission to ICU, and use of a rescue medication for any reason);
- Primary Endpoint for phase 3: Composite endpoint of death and clinical severe events (the subject dies or requires invasive mechanical ventilation use and/or admission to ICU).

3.5.2 Secondary Endpoints:

- Clinical severity score (a seven-category ordinal scale) at any available time point
- Dyspnea severity (Liker categorical scale and VAS continuous scale) at any available time point;
- Changes in body temperature at any available time point;
- Duration and quantity of supplemental oxygen treatment at any available time point;
- Incidence and duration of mechanical ventilation use at any available time point;
- Incidence of ICU admission need at any available time point;
- Lung damage extension changes from baseline (assessed by Chest CT or Rx) at any available time point;
- Change from baseline in lung exudation degree (assessed by Chest CT or Rx) at any available time point;
- PaO₂ at any available time point;
- SpO₂ at any available time point;
- Partial arteriolar oxygen pressure (PaO₂) to fraction of inspiration O₂ (FiO₂) ratio at any available time point;
- CRP at any available time point;
- Hs-CRP at any available time point;

3.5.3 Exploratory Endpoints (not mandatory):

- Cytokine profile at any available time point;

- Concentration of reparixin in serum over time;
- SARS-CoV-2 virologic counts at any available time point.

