4.6 DMC Safety Integrity Review

In addition to the above interim analyses, analysis of safety data will be performed for supporting Safety Integrity Review meetings during the trial.

Safety Integrity Review meetings will be performed on ongoing basis (frequency will be defined by DMC members also considering feedbacks from REPAVID-19 Investigators) and at the end of the phase 2 in order to ensure that, in addition to superiority in efficacy, reparixin has an adequate safety profile.

The following information will be analyzed for safety reason at each Safety Integrity Review:

- Major protocol changes,
- Information on subject screening,
- Study accrual by month and by institution,
- Eligibility violations,
- Demographics,
- Length of follow-up data available (pooled by treatment regimen),
- Analyses of adverse events,
- Analyses of vital signs, including basic summaries and longitudinal analyses,
- Analyses of lab values, including basic summaries and longitudinal analyses,
- Discontinuation of medications,
- Information on crossover subjects.

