7.1.3 Sensitivity analysis

7.1.3.1 Phase 2

Results of primary analysis will be assessed in sensitivity analyses as detailed below.

- The comparison between treatment and control will be performed by means of a Cox regression model, using age class, gender and clinical severity score at baseline as covariates, to assess the robustness of results on primary endpoint versus the presence of confounding factors. Additional covariates might be included after DRM in case relevant baseline imbalance will be identified between groups, despite randomization. The assumptions of proportionality will be investigated with a time-dependent exploratory variable, which is defined as $\text{treatment} * \{\log[\text{time to event}]\}$. If the p-value from the Wald Chi-squared statistic for this variable is less than 5% there is evidence of a departure from the adjusted model assumptions. In case of non-proportional hazards, a Weibull model will be assumed as parametric form of the distribution of survival times. The treatment group will be included in the model as covariate.
- Time to event for each single component of the primary endpoint will be performed separately in order to adjust for the presence of possible competing risks. The following events:
 - first supplemental oxygen requirement,
 - first mechanical ventilation use,
 - first admission to ICU, and
 - first use of a rescue medication for any reason

will be analyzed according to survival analysis methodology detailed in section 4.1 with the following modifications:

- the common representation of survival curves using the Kaplan-Meier estimator will be replaced by the cumulative incidence function,
- the presence of other competing event(s) is/are treated as censored.
- A modified composite endpoint of phase 2 will be analyzed adding “death” as fifth component. It will be analyzed according to section 7.1.2 to assess the robustness of results on primary endpoint versus the presence of censoring due to fatal events.

Decision to proceed/not proceed to phase 3 will be based only on primary analysis results, despite inconsistencies with sensitivity analyses. Sensitivity results will be interpreted and discussed in the clinical study report and will be used to eventually adjust adaptations for the phase 3.

7.1.3.2 Phase 3

Results of primary analysis will be assessed in sensitivity analyses as detailed below.

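### Protocol 9.4.5 ties its only outcome-specific harm criterion to reoperation after surgery, in a drug trial with no study surgery, and the only deaths it names are in the control group

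*Protocol*

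**What the plan says.** Protocol 9.4.5 describes how the DMC may recommend stopping for safety. It begins generally: the DMC is to reconsider continuation "if there is emerging evidence that Reparixin is harmful". It then says that a safety termination should rest on all the data together, "including the number of unexpected deaths in the control group", along with the evidence on efficacy and the overall safety profile. The next sentence gives the one criterion linked to a specific outcome. Stopping early comes into question where this holds: "rate of clinically significant post-surgical complications that require reoperation reliably exceeds the rate expected currently in standard practice settings". The section also allows stopping for poor trial conduct and sets efficacy and non-binding futility boundaries on the primary endpoint.

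SAP 4.6 introduces its list of DMC safety data with "The following information will be analyzed for safety reason at each Safety Integrity Review". The list includes adverse events, vital signs, laboratory values, discontinuations and crossover subjects. It has no separate item for deaths and no rule for stopping for harm. SAP 3.4 refers to a further document: "analyses for safety integrity reviews will be performed according to DMC charter". That charter is not among the documents.

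**The concern.** A DMC reading 9.4.5 for guidance on harm finds one named outcome, and it belongs to a different kind of trial. Patients here are hospitalised with severe COVID-19 pneumonia and receive oral reparixin or standard of care, with IV reparixin planned only as phase 3 rescue for controls. Reoperation is not a harm that this treatment or disease would be expected to produce.

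The one mention of deaths is also badly aimed. A count of control-group deaths has no comparator, and harm from reparixin would be expected as an excess in the other arm. Limiting the count to unexpected deaths narrows it further in a disease where death from progression is foreseeable.

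What is at stake is the clarity of the written harm guidance in an open-label trial, chiefly in phase 2, where the interim test of the primary endpoint does not count death.

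**Working it through.** No arithmetic applies. The reoperation criterion carries no numeric rate, and nothing here depends on alpha, power or event counts. The check is a reading of the sections against each other.

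**1. Statements in Protocol 9.4.5 on safety or early termination**

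| Statement | Type | Outcome named |
|---|---|---|
| Emerging evidence of harm from reparixin | General harm | None |
| Possible interruption of one route of administration | General | None |
| All data weighed together | General, with examples | Unexpected control-group deaths |
| Reoperation rate above standard practice | Specific harm criterion | Post-surgical complications |
| Poor trial conduct | Not harm | None |
| Efficacy and futility boundaries | Not harm | Primary endpoint |

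Count: one outcome-specific harm criterion (surgical), one mention of deaths (control group), no numeric harm threshold.

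**2. Does the specific criterion fit the trial?** Protocol 4.1, 4.2, 5.2 and 6.1 define the population and treatments. None includes a surgical procedure. An incidental surgical complication would still be recorded as an AE or SAE, but it is not a relevant basis for stopping.

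**3. Does the SAP correct it?** No. SAP 4.6 lists data for review without a harm rule. Table 6 in SAP 4.7 gives only unspecified safety reasons as the trigger for changing the route or the allocation ratio.

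**4. Where does death enter in phase 2?**
- Primary composite (SAP 3.5.1): "supplemental oxygen requirement, invasive mechanical ventilation use, admission to ICU, and use of a rescue medication for any reason". Death is in 0 of 4 components, against 1 of 3 in the phase 3 composite. A patient who dies with no earlier component event is therefore not an event in the phase 2 primary test.
- Sensitivity analysis (SAP 7.1.3.1): "A modified composite endpoint of phase 2 will be analyzed adding" death as a fifth component.
- Secondary analysis (SAP 7.1.2): each phase's primary endpoint is also analysed as a secondary in the other phase, so the composite containing death is analysed in phase 2.
- Clinical severity score (Protocol section 3): death is category 7.
- Safety (SAP 8.1): number of deaths, TEAEs leading to death, and a listing of deaths. Table 7 in SAP 9.1 also derives overall survival.

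So death is not tested directly at the phase 2 interim, but it is far from absent from the phase 2 analyses.

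**5. Can deaths by randomised arm be obtained?** Yes. SAP 4.3 puts adverse event tables in the Safety set, which SAP 4.2.3 groups by actual treatment. The same section makes the Randomized set the default for listings, showing both planned and actual treatment. The listing of deaths therefore already identifies each death by planned arm. What is not listed in SAP 4.6 is a ready n/N comparison for the DMC.

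**The case against.** The strongest reply is that this is a stray sentence with no practical effect. The opening harm clause points to the right arm. Control-group deaths are an example within a wider weighing of evidence, not a trigger, and nothing asks the DMC to read them alone. Protocol 7.3.1 states "Death shall always be reported as SAE", so every death falls within the adverse event analyses that SAP 4.6 gives the DMC. The charter may already call for deaths by arm. Nearly all of this stands, and it is why the point is minor. It does not make the reoperation criterion apply, or a control-only death count informative about reparixin.

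A reader might infer more from the wording, in three ways that the documents do not support:
- *That the DMC cannot stop for harm, or is directed to the wrong arm.* The general clauses leave it free to act on any harm in either arm.
- *That death enters phase 2 only through a sensitivity analysis.* The secondary analysis of the phase 3 composite, the severity score and the safety outputs all include it.
- *That every death output uses the Safety set, so randomised comparisons are unavailable.* The listing default says otherwise. In phase 2, moreover, reparixin is not the planned rescue, and Protocol 9.3 counts standard of care as a treatment received, so actual and randomised arms should nearly coincide.

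**Conclusion.** The point holds as a minor drafting error in the DMC guidance. The only outcome-specific harm criterion in Protocol 9.4.5 does not apply to this trial, and the only deaths it names cannot on their own show harm from reparixin. Neither SAP 4.6 nor SAP Table 6 corrects this.

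Its size is limited to wording: no type I error, power, sample size or data collection changes. The conclusion about 9.4.5 rests on its text alone. Whether the DMC actually lacks a comparison of deaths by arm is not established, because that depends on the unseen charter.

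**What to change.** 1. In Protocol 9.4.5, delete the sentence on reoperation.
2. In the same section, replace "including the number of unexpected deaths in the control group" with: *including all deaths and SAEs compared between the arms*.
3. Unless the DMC charter already provides it, add to the SAP 4.6 list: *deaths by randomised arm (n/N, %)*.

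Date of death and SAEs are already collected, and the listing of deaths already carries planned treatment. The cost is two wording changes, one added line and one simple table. SAP 4.7 requires a protocol amendment and SAP update before phase 3, so the text can be corrected then at the latest. Because the point matters most in phase 2, the DMC should be given the comparison for its phase 2 reviews without waiting for that amendment.

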# 9 STATISTICAL CONSIDERATIONS

#### 9.1 Sample size

The sample size for this trial will be adaptively determined through a phase 2/3 design. Enrollment is planned to last approximately 2 months. Each patient will be randomly allocated to Reparixin or Control according to a randomization ratio of 2:1 and he/she will be followed for the entire treatment and follow-up duration for collecting the efficacy endpoints of each study phase.

For the Phase 2 portion of the study, the primary analysis will compare Reparixin versus Control in terms of time to a composite endpoint (primary endpoint of phase 2) including the following events: requirement of supplemental oxygen treatment, mechanical ventilation use, admission to ICU, and any requirement of rescue medication. Based on clinical experience, an improvement of the median time freedom from composite event of 1.5 times is expected. Assuming an exponential distribution, a total sample size of 48 patients will allow to provide 80% power to show superiority of Reparixin compared to control using a log-rank test at a one-sided significance level of 0.025.

The sample size for the phase 3 is based on assessment of superiority of Reparixin compared to control arm in terms of freedom from a composite endpoint (primary endpoint of phase 3) of severe events including death, admission to the ICU, requirement of mechanical ventilation.

Based on same assumptions of phase 2 regarding randomization (2:1) and expecting to double the median time freedom from severe composite event using Reparixin compared to control (from 2-4 to 4-8 days), a total sample size of 111 patients will allow to achieve a power of 90% to show superiority of Reparixin over control using a log-rank test at a one-sided significance level of 0.025. No drop-out are expected to happen. The number of patients to be included may be revised based on considerations from Phase 2 data analysis.

Primary endpoint of phase 3 will be tested only if superiority of Reparixin is shown in phase 2. Thus, the overall type I error of the study will be controlled at 0.025 via the hierarchical testing procedure.

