4.1 General

Appropriate descriptive statistics will be produced, according to the variable:

- for continuous data n , mean, standard deviation (SD), median, Q1-Q3, and range (minimum and maximum) will be presented;
- for categorical data, frequency distributions and percentages will be presented;
- for time-to-event variables, cumulative freedom from event will be evaluated using Kaplan-Meier (KM) method. The degree of uncertainty will be expressed with 95% confidence limits (calculated per the method proposed by Greenwood³). Comparison of curves among arms will be performed with the log-rank test. KM graphs will be presented along with the number of subject-at-risk at exact time points. Subjects who have discontinued/terminated the study without an event will be censored at the date of study discontinuation/termination. Subjects ongoing and who are free from event at the time of database lock (for example at interim analyses) will be censored at the last available date.

Unless otherwise specified, hypothesis testing will be carried out at the $\alpha = 0.050$ level (two-sided) when comparing treatments. For all inferential analyses, p-value will be rounded to three decimal places. Statistical significance will be declared if the rounded p-value will be less than or equal to 0.050. For primary analysis only (section 7.1.2), p-values will be provided at 5th decimal place, in order to compare with efficacy and futility thresholds specified in section 4.5.

Additional post-hoc analysis may be produced to further allow comparison between reparixin and control, according to the results obtained. Any unplanned analyses as well as deviations from the original statistical plan will be clearly documented in the Clinical Study Report.

Derivation rules for efficacy and safety analyses are reported in Table 7 in section 9.

All the data collected and derived in the study will be presented in subject data listings by centre.

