4.5 Interim analyses

Interim analyses are planned at specific time point during phase 2 and phase 3 for identification of early superiority of reparixin (efficacy) or for early stop of the trial for futility.

O'Brien-Fleming spending functions will be used to control the type I and II errors for analyses of primary endpoints. P-values boundaries for efficacy and futility at interim and final analyses for phase 2 and phase 3 are reported in Table 4 and Table 5, respectively.

Table 4: O'Brien-Fleming spending functions boundaries for primary analysis in phase 2

Analysis	Sample Size	Boundaries for primary endpoint	
		Efficacy	Futility
Interim #1	~27 (23 events)	p-value < 0.00258	p-value ≥ 0.23349
Final	48 (46 events)	p-value < 0.02400	p-value ≥ 0.02400

Table 5: O'Brien-Fleming spending functions boundaries for primary analysis in phase 3

Analysis	Sample Size	Boundaries for primary endpoint	
		Efficacy	Futility
Interim #1	~60 (60 events)	p-value < 0.00296	p-value ≥ 0.26674
Interim #2	~81 (81 events)	p-value < 0.00892	p-value ≥ 0.09841
Final	111 (109 events)	p-value < 0.02151	p-value ≥ 0.02151

The interim analyses will be conducted by DMC who will communicate to the Sponsor the result of the interim analysis and the consequent decision on the continuation of the study.

The following scenarios may emerge from the interim analysis:

- the communication from the DMC to the Sponsor will be "Not enough evidence for demonstrate superiority of reparixin". Since results are not considered enough to draw conclusions on primary

endpoints, the study enrolment will continue up to the next analysis step, and treatments and follow-ups will proceed without modifications.

- the communication from the DMC to the Sponsor will be “Superiority of reparixin is shown”. In this case, the following action will be taken according to the study phase:
 - Phase 2:
 - enrollment of subjects in phase 2 is stopped
 - already enrolled subjects continue their residual treatment and follow-up as planned
 - adaptation of phase 3, if needed;
 - enrollment of subjects in phase 3 may start;
 - Phase 3:
 - enrollment of subjects is stopped
 - already enrolled subjects continue their residual treatment and follow-up as planned
 - when last enrolled subject completes the follow-up and database is close, final analysis is performed and clinical study report will be released.

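### The interim and final p-value thresholds are classical O'Brien-Fleming bounds, not the spending-function bounds the plan names, and the phase 3 set fits a denominator of 111 instead of the SAP's 109 events

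*Protocol*

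**What the plan says.** Protocol 9.4.5 and SAP 4.5 name one method for both error types: "O'Brien-Fleming spending functions will be used to control the type I and II errors for analyses of primary endpoints". Protocol 9.4.2.1 and 9.4.2.2 and SAP 7.1.1 repeat that the thresholds are calculated that way. The test is set up "using a log-rank test at a one-sided significance level of 0.025" (Protocol 9.1), and the futility rule is "for an early stop of the trial for futility (nonbinding").

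The same p-values stand in Protocol Tables 1 and 2 and in SAP Tables 4 and 5:

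| Look | Subjects | Events (SAP) | Efficacy | Futility |
|---|---|---|---|---|
| Phase 2 interim | ~27 | 23 | 0.00258 | 0.23349 |
| Phase 2 final | 48 | 46 | 0.02400 | 0.02400 |
| Phase 3 interim 1 | ~60 | 60 | 0.00296 | 0.26674 |
| Phase 3 interim 2 | ~81 | 81 | 0.00892 | 0.09841 |
| Phase 3 final | 111 | 109 | 0.02151 | 0.02151 |

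The protocol indexes the looks by sample size only. The SAP adds events, ending phase 3 at "111 (109 events"), and SAP 3.4 times the phase 3 looks at "approximately 55% and 74% of the planned severe events of primary endpoint of phase 3 has happened". SAP 4.1 reports the primary p-values to five decimals "in order to compare with efficacy and futility thresholds specified in section 4.5".

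**The concern.** An error-spending function and the classical O'Brien-Fleming boundary are different designs. A spending function fixes how much type I error may be used by a given fraction of the information, so a bound can be recomputed from whatever event count a look actually has. The classical boundary fixes the shape of the critical values and is exact only at the fractions for which it was solved.

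These numbers decide whether phase 2 stops, whether phase 3 opens and whether superiority is claimed. A statistician who implements the named method will not obtain the printed table, and a phase 2 interim p-value between 0.00153 and 0.00258 leads to opposite decisions. For the log-rank test the information is the number of events, so the phase 3 bounds should rest on the SAP's 109.

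**Working it through.** **Inputs.** One-sided alpha is 0.025 (Protocol 9.1). Power is 80% for phase 2 ("a total sample size of 48 patients will allow to provide 80% power") and 90% for phase 3 (Protocol 9.1; SAP 3.2 says only above 80%). Looks are at 23/46 events and at 60, 81 and 109 events (SAP 4.5). Allocation is 2:1. All bounds come from numerical integration of the group-sequential normal distribution.

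**1. Reproduce the printed values.** The classical boundary is z_k = C/√t_k, with C solved so that the total one-sided crossing probability under the null is 0.025.

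- Phase 2, t = (0.50, 1): C = 1.9774. Then 1.9774/√0.50 = 2.797, giving p = 0.00258, and 1.9774 gives p = 0.02400. Both agree with Table 1.
- Phase 3, t = (60/111, 81/111, 1): C = 2.0236, giving 0.00296, 0.00892 and 0.02151. All three agree with Table 2, including "p-value <0.00296" at the first look.
- The matching classical nonbinding futility bounds are 0.23349 (80% power) and 0.26674/0.09841 (90% power), again as printed.

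**2. Recover the information fractions from the table.** For a classical boundary, t_k = (z_final/z_k)².

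- Phase 2: (1.9774/2.7969)² = 0.4998. This is 23/46. The patient fraction 27/48 would give a first bound of 0.00404.
- Phase 3: (2.0235/2.7522)² = 0.5406 and (2.0235/2.3689)² = 0.7296. Here 60/111 = 0.5405 and 81/111 = 0.7297, whereas 60/109 = 0.5505 and 81/109 = 0.7431.

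**3. Compute the named method.** The O'Brien-Fleming-type spending function is α(t) = 2[1 − Φ(z/√t)] with z = Φ⁻¹(1 − 0.0125) = 2.2414. At t = 0.50 it spends 2[1 − Φ(3.170)] = 0.00153.

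| Efficacy bound | Printed | Spending, on events | Classical, on events |
|---|---|---|---|
| Phase 2 interim | 0.00258 | 0.00153 | 0.00258 |
| Phase 2 final | 0.02400 | 0.02450 | 0.02400 |
| Phase 3 interim 1 | 0.00296 | 0.00252 | 0.00316 |
| Phase 3 interim 2 | 0.00892 | 0.00854 | 0.00937 |
| Phase 3 final | 0.02151 | 0.02204 | 0.02137 |

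Other spending forms tried at 23/46 also miss the printed pair: two-sided 0.05 halved gives 0.00279/0.02389, a cubic power family 0.00312/0.02371, and the gamma family with parameter −4 gives 0.00298/0.02379.

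**4. Type I error of the printed efficacy bounds.**

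- At plan: 0.0250 in phase 2, and 0.02485 in phase 3 at 60/109 and 81/109.
- Phase 2 look moved to 30%, 40% or 60% of events: 0.0256, 0.0253, 0.0247.
- Phase 3 looks moved to 40% and 60%: 0.0266. The off-plan timings are illustrations, not figures from the documents.

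**5. Chance of a phase 2 interim efficacy stop.** The drift at full information is √(46 × 2/9) × |ln HR|, and at the interim it is multiplied by √0.50.

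- SAP 3.2 (2 versus 5 days, HR 0.4): drift 2.930, interim 2.072. Then 1 − Φ(2.797 − 2.072) = 23.4% with the printed bound, and 1 − Φ(2.962 − 2.072) = 18.7% with the spending bound.
- Protocol 9.1 (1.5-fold median, HR 1/1.5): drift 1.296, interim 0.917. The corresponding chances are 3.0% and 2.0%.

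**6. Overall power, efficacy bounds only.** Phase 2 at HR 0.4: 83.1% printed against 83.3% spending. Phase 3 at HR 0.5: 92.1% against 92.2%.

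**The case against.** The strongest reply is that nothing is operationally unclear. The thresholds are prespecified, identical in protocol and SAP, and the analyst is told to compare the p-value with them, so nobody has to derive a bound. They form a genuine O'Brien-Fleming boundary, overall power barely moves, and the phase 3 table is provisional. Much of this stands. At the planned looks the printed numbers define a valid test.

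A reader might infer that the 0.025 level is breached. The documents do not support that: at the planned looks the error is 0.0250 and 0.02485, the second slightly conservative. Excess appears only if a look comes well before its planned event count. The phase 2 look is set at half of the events, and the approximate 27 beside it is a subject count, so it is not evidence of drift. Only the phase 3 timing is described as approximate.

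A reader might also take it as established that phase 3 was computed on patients. That is an inference from the five-decimal match. The SAP gives 60 and 81 as both subjects and events, so only the final denominator separates the two scales. Protocol 9.2 times the analysis when all planned subjects have had the event, and 9.1 assumes no drop-out, so 111 may have been meant as 111 events. The phase 2 table does not share the problem.

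What the reply leaves unanswered is that the text names a method that does not produce the table, that the SAP kept the phase 3 p-values while stating 109 final events, and that no rule covers a look at a different event count.

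**Conclusion.** The concern holds as a mismatch between the stated method and the tabulated one, with a separate inconsistency in the phase 3 information scale. It is not a failure of type I error control at the planned looks.

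The largest discrepancy is the phase 2 interim efficacy bound, 0.00258 against 0.00153, a factor of 1.7. It changes the chance of an interim efficacy stop by 4.7 percentage points under the SAP's hazard ratio of 0.4, but by only about 1 point under the protocol's 1.5-fold median, so its size depends on which of the two stated effects is used. In phase 3 the printed bounds differ from the spending values by less than 0.001 at every look. The practical effect is modest. It still merits correction because these are the decision thresholds, compared at five decimals, and fixed values do not hold 0.025 exactly when a look is off plan.

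The efficacy results rest on one-sided 0.025 and the SAP's event counts. The futility results also assume 80% and 90% power and a nonbinding rule.

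**What to change.** Before the relevant look, take one of two routes.

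(a) Keep the spending function. State its formula, take 46 and 109 events as full information, and recompute each bound from the actual event count. Print as planned values:

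- Phase 2: efficacy 0.00153/0.02450, nonbinding futility 0.288.
- Phase 3: efficacy 0.00252/0.00854/0.02204, nonbinding futility 0.284/0.106.

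These futility values are solved so that the efficacy and futility bounds meet at the final look with 80% and 90% power. State that convention, because fixing the drift at the assumed effect instead gives different values whose bounds do not meet at the end.

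(b) Name the classical boundary. Keep Table 1 (SAP Table 4), correct phase 3 on 60/109 and 81/109 to efficacy 0.00316/0.00937/0.02137 and futility 0.253/0.091, and state how bounds are recomputed if the event count at a look differs from plan.

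Either route needs only table and wording edits and no extra patients. Under (a) the interim efficacy hurdle is slightly stricter and the final one slightly easier. The phase 3 correction can go into the protocol amendment and SAP update that SAP 4.7 already requires before phase 3. If a look has already taken place, keep the bound that was used and report the method behind it.
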